9.4.3 Analysis of the Secondary Endpoint(s)

Hypothesis: Differences in the stool metabolome, including increased primary bile acids and decreased short chain fatty acids, will be found in post-treatment samples compared to pre-treatment samples.

In order to quantify changes in the stool metabolome with BSS treatment over approximately a 1-month period, we will examine the following comparing the baseline metabolome (pre-BSS treatment) with post-treatment samples at each time point:

- Untargeted metabolomic analysis will be performed on serial stool samples by liquid chromatography and high-resolution tandem mass spectrometry. Metabolites will be identified by comparison to library entries of purified standards or recurrent unknown entities. In addition, as short chain fatty acids and bile acids are of particular interest, a separate targeted analysis for these will be performed.
- Metabolites will be compared pre-treatment to approximately 1 month post-treatment. Identified metabolites will be quantified by peak integration. Data will be scaled to a median of 1 for each biochemical in that sample set. Probabilistic principal component

analysis will be used to select for discriminative metabolites among pre-treatment and post-treatment sample. If significant differences in metabolites are found in the early time points post-treatment, as per murine models, then we can longitudinally examine post-treatment samples to determine the length of time these differences last.

- In a multi-omic data analysis, metabolite changes will be correlated with microbiome changes to assess which bacterial taxa may be driving the metabolite changes found.

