3 OBJECTIVES AND ENDPOINTS

OBJECTIVES	ENDPOINTS	JUSTIFICATION FOR ENDPOINTS
Primary		
To evaluate the effect of BSS on the human gut microbiome.	Differences in the relative abundance of taxa in stool samples pre-BSS and approximately 1 month post-BSS. Differences in microbiome metrics of alpha diversity and beta diversity will also be assessed.	Hypothesis: there will be a decrease in beneficial bacterial taxa (eg, Lactobacillus) and increase in potential pathobionts (eg, Enterococcus). This will be most pronounced at day 2 (the day after therapy) and some changes may persist up to 1 month. This hypothesis is based on our findings in murine models (section 2.2.). These specific endpoints of relative abundance of taxa, alpha diversity, and beta diversity were chosen as they are standard metrics to assess changes in the microbiome.(28, 29)

OBJECTIVES	ENDPOINTS	JUSTIFICATION FOR ENDPOINTS
Secondary		
To evaluate the effect of BSS on the human gut metabolome.	Differences in the stool metabolome (including short chain fatty acids, bile acids, and untargeted metabolomics) pre-BSS and approximately 1 month post-BSS.	Hypothesis: there will be a change in specific stool metabolites (eg, a decrease in protective secondary bile acids and short chain fatty acids) with BSS therapy. This will correlate with gut microbiome changes. Stool metabolites are produced by gut microbiota and also contain host products. Importantly, they can assess the function of the microbiota, ie, “what are they doing” rather than just “what’s there.”(30) Moreover, bacterial metabolites have a key role in gut barrier function, host immunity, and inflammation, which is important in this study when assessing microbiome and host responses to BSS.(31) Targeted assays for metabolites of special interest, such as bile acids, short chain acids, and sulfides may be performed.(32, 33) Wide targeted or untargeted metabolite assays will also be performed to uncover other metabolites of relevance.
Tertiary/Exploratory		

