4.2 SCIENTIFIC RATIONALE FOR STUDY DESIGN

In our murine models, BSS caused a profound effect in the gut microbiome with subsequent changes in the host response. As there are no data on the effect of BSS on the human gut microbiome, an open-label pilot study is needed to gather preliminary data. The study design is strengthened by comparing the microbiome within a same individual before and after intervention as previously reported in other studies of the gut microbiome.(37) Moreover, in our murine models, longitudinal microbiome changes were seen within individual mice, in addition to between control and treatment groups. If an effect is seen, this lays the foundation for confirmation in a study with a randomized control design and further studies to assess the clinical impact and potential health outcomes of these changes in humans.

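### The only method named for picking metabolites that separate pre- from post-BSS stool is unsupervised and unpaired, so it can miss small or moderate effects, and no test or error control is specified

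*Combined protocol and SAP*

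**What the plan says.** Section 3 defines the secondary endpoint as "Differences in the stool metabolome (including short chain fatty acids, bile acids, and untargeted metabolomics) pre-BSS and approximately 1 month post-BSS". Section 9.4.3 then gives the analysis:

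- Contrast: "Metabolites will be compared pre-treatment to approximately 1 month post-treatment". The section also announces comparisons at each time point. No test or model is attached to either.
- Preparation: "Data will be scaled to a median of 1 for each biochemical in that sample set". No log transform and no centring within participant is stated.
- Selection: probabilistic principal component "analysis will be used to select for discriminative metabolites among pre-treatment and post-treatment sample".
- Trigger for the longitudinal follow-on: "If significant differences in metabolites are found in the early time points post-treatment". No criterion for significance is given.
- Bile acids and short chain fatty acids: "a separate targeted analysis for these will be performed", again with no test named.
- A final multi-omic step correlates changes in metabolites with changes in the microbiome.

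The rest of the plan does not fill the gap. The paired t-test in section 9.2 is assigned to the primary endpoint. Section 9.4.1 promises means or proportions with 95% confidence intervals, does not say that these are for paired changes, and reserves its more advanced methods for the microbiome data.

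**The concern.** The design is single-arm, so its information about BSS lies in how each person changes. Section 4.2 makes this argument for the microbiome: "The study design is strengthened by comparing the microbiome within a same individual before and after intervention". The method named for choosing metabolites does not use that strength. Probabilistic PCA describes the total covariance of the pooled samples, and stool from different people can differ for many reasons unrelated to BSS. If that variation dominates, the leading components describe people and not treatment.

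Two things are at stake. Real within-person changes of modest size could be passed over. And a statement that metabolites differ significantly would have no defined error rate, although the untargeted panel is where many comparisons are made and the result decides whether the longitudinal question is pursued.

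**Working it through.** **No figure to reproduce.** The plan gives no sample size, power or alpha for the secondary endpoint. The calculations in section 9.2 concern *Lactobacillus* only.

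**What the method sees.** Probabilistic PCA fits x = Wz + μ + ε, with ε ~ N(0, σ²I), to 20 × 2 = 40 samples treated as independent. Visit and participant do not enter the model.

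**Inputs.** N = 20 is from section 9.2. Everything else is assumed and varied: 500 metabolites on a log scale; between-person SD 1 (half of that variance from five shared factors) or about 1.2; within-person SD 0.5 or 1; 25 or 100 metabolites truly shifted.

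**Why the leading components can miss the effect.** If k metabolites shift by δ, and half the samples are post-treatment, the variance along the treatment direction is about kδ²/4. With between-person SD 1, each shared factor carries on average 0.5 × 500 / 5 = 50.

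- k = 25, δ = 0.5: 25 × 0.25 / 4 = 1.6
- k = 25, δ = 1: 25 × 1 / 4 = 6.25
- k = 100, δ = 1: 100 × 1 / 4 = 25
- k = 100, δ = 2: 100 × 4 / 4 = 100
- k = 100, δ = 3: 100 × 9 / 4 = 225

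Only the last two clearly exceed 50. A paired test does not face this competition. The SD of a within-person change is 0.5 × √2 = 0.71 whatever the between-person SD.

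**Simulation, 25 of 500 shifted, within-person SD 0.5.** Ranges span the runs under the two between-person settings.

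| Shift | Leading-component loadings: true metabolites in top 25 (chance 5%) | Paired t with Benjamini-Hochberg at 0.05: true metabolites found |
|---|---|---|
| 0.5 | 5% | 23% to 27% |
| 0.75 | 5% | 86% to 87% |
| 1.0 | 5% to 6% | 99% |

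The realised false discovery rate of the paired approach was about 4% to 5%. The two columns measure different things: the first assumes that the number of true changes is known, and the second does not. Like for like, ranking by paired t puts 68% (shift 0.5) and 98% (shift 1.0) of the true metabolites in the top 25.

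**Sensitivity of the pooled PCA result.**

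- Larger shifts, still 25 metabolites: 6% at shift 2 and 20% at shift 3.
- Within-person SD 1, 25 metabolites: 5% at shift 1 and 6% at shift 2 (paired with Benjamini-Hochberg: 24% and 100%).
- Median-1 scaling without a log transform: 5%, 6%, 7% and 12% at shifts 0.5, 0.75, 1.0 and 2.0.
- 100 metabolites shifted (chance 20%): 20% at shift 1, 72% to 82% at shift 2, 99% to 100% at shift 3.
- Choosing, out of all components, the one whose scores best separate pre from post: 64%, 92% to 93% and 99% at shifts 0.5, 0.75 and 1.0. Searching only the first 10 components (at shift 0.75) still gave about 5%.
- Subtracting each person's mean before the PCA: 56%, 95% and 99% at shifts 0.5, 0.75 and 1.0.

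**The case against.** The strongest reply is that the 5% figure depends on reading the selection as a ranking by leading-component loadings. Section 9.4.3 does not say how many components are kept or how loadings become a list. An analyst aiming to discriminate pre from post might look for the component that separates them, or centre within person, and would then do about as well as a paired ranking. This stands as a limit on the size of the problem. It does not rescue the text: both steps bring in the label or the pairing from outside the named method, neither is written down, and neither yields an error rate.

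A reader might infer that the plan is bound to select between-person variation instead of BSS effects, so that its list would be little better than a random draw. The documents do not support that. The outcome depends on variances, metabolite numbers and effect sizes that they do not give, and a large, broad effect does reach the leading components.

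A reader might also infer that the whole secondary endpoint rests on probabilistic PCA. It does not. A separate targeted analysis covers the bile acids and short chain fatty acids named in the hypothesis, and summaries are planned as well, though with no stated paired test. Nor does the plan say that the multi-omic correlations are restricted to a PCA-selected list, so a wrong list feeding that step is conjecture.

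Finally, the study calls itself exploratory and a pilot, with confirmation left to a randomized study. This lowers the consequence. It does not supply the missing test for a declared secondary endpoint with a directional hypothesis.

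**Conclusion.** The concern holds in a bounded form. Section 9.4.3 gives probabilistic PCA a task that it cannot do by itself, and the reference to significance has no test, pairing or error control behind it. That part follows from the text and needs no assumption.

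The loss does rest on assumptions. For 25 of 500 log-scale metabolites shifted by 0.5 to 1.0, with between-person SD 1 to 1.2 and within-person SD 0.5, leading-component loadings perform at chance (about 5%), against about 25% to 99% for paired tests with Benjamini-Hochberg. In the settings tried, pooled PCA passed 70% only when the effect was both large and widespread. The unstated steps, picking the component by label from all components or centring within person, raise recovery to roughly 55% to 99% at these shifts. The defensible conclusion is that small or moderate BSS effects can be masked, not that they must be. The paired approach has limits too: at a shift of 0.5 it finds only about a quarter of the true changes once the false discovery rate is controlled.

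**What to change.** Amend section 9.4.3 as follows.

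1. For each metabolite, test the log-scale within-person change from pre-BSS to day 28 with a paired t or signed-rank test, or fit a mixed model with a participant effect over all visits. The mixed model also uses participants who lack a day 28 sample, which matters because section 8.2.1 accepts that stool may be missing at some visits. Name the pre-BSS reference, since section 1.3 collects stool both at baseline and at day 0 before dosing.
2. Control the false discovery rate across the untargeted panel, for example Benjamini-Hochberg at 5%, and define significance for the longitudinal trigger by that rule.
3. Test the targeted bile acids and short chain fatty acids with the same paired approach, as a separate, prespecified small family.
4. Keep probabilistic PCA for display only. Centring within person first would make the display more informative.

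The cost is SAP wording and routine analysis code. No samples, visits or participants are added.

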9.4.4 Safety Analyses

As this study uses BSS, an already FDA-approved OTC medication, there are no safety endpoints that will be analyzed. However, safety will be assessed throughout the study as per section 8.3.

For the possible true probabilities of AEs described in the pausing rules (section 7.1.1), Table 2 below lists the early stop probabilities for the first 10 participants.

Table 2: Probability of Early Stop for Possible True Probabilities of Any Adverse Event in the First 10 Participants

True prob. of any AE	0.01	0.05	0.10	0.2	0.3	0.4
Prob. of ≥ 1 with any AE in the first 10 participants	0.10	0.40	0.65	0.80	0.97	0.99

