
AE, adverse event; BSS, bismuth subsalicylate; CBC/diff, complete blood count with differential; ECG, electrocardiogram; GI, gastrointestinal; PT/PTT/INR, prothrombin time, partial thromboplastin time, and international normalized ratio; X, to be performed.
 
a Baseline will be done after confirmation of eligibility. The overlap between the screening and baseline windows accounts for the required 30-day interval between the optional colonoscopies at baseline and day 8. Participants who do not undergo colonoscopy may have a shorter interval between screening, baseline, and day 0.
 
b The informed consent form will be signed before any research procedures are conducted on this study.
 
c Limited review of existing medical records may be done before the participant signs the informed consent form.
 
d Continued eligibility will be confirmed at the baseline visit.
 
e For participants of childbearing potential only. If the visit will be done remotely, then the participant will be instructed to send a urine sample to the study team, which will be used for pregnancy testing.
 
f For participants who will have the baseline colonoscopy, the timing of baseline pregnancy test will be per Department of Perioperative Medicine guidelines.
 
g To avoid repetition of procedures, pregnancy test will only be done at day 0 if baseline was more than 14 days before.
 
h Pregnancy test will only be done at day 8 if the participant will undergo the colonoscopy.
 
i Day 0 stool, which will be collected before first dose of BSS, may be collected up to 7 days earlier. For participants undergoing colonoscopy, stool samples will be attempted to be collected prior to the start of the bowel preparation.
 
j These procedures will only be done if the participant is undergoing the colonoscopy and the procedures are determined to be needed per the Department of Perioperative Medicine guidelines at the NIH Clinical Center. These labs will be repeated for the second (day 8) colonoscopy per the Department of Perioperative Medicine and if there are more than 30 days between it and the first procedure. For the convenience of the participant and study team, blood for the second colonoscopy may be drawn at the day 0 or 2 visits (the latter only if in person at the NIH Clinical Center).
 
k These procedures will only be done if the participant is undergoing the colonoscopy.
 
l Research blood draw is optional and will only be offered at in-person visits.
							

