Venipuncture: The risks of drawing blood include pain, bruising, bleeding, fainting, and, rarely, infection. The amount of blood drawn for research purposes will be within the limits allowed for adult research participants by the NIH CC (Medical Administrative Policy 95-9, Guidelines for Limits of Blood Drawn for Research Purposes in the Clinical Center: <http://cc-internal.cc.nih.gov/policies/PDF/M95-9.pdf>).

Colonoscopy with biopsies and brushings: Serious risks of colonoscopy with biopsy and brushings include perforation, severe bleeding, and serious infection. These risks are rare. The risk of perforation is increased in people who have had perforation in the past, so people with a history of GI perforation will be excluded from colonoscopy. In addition, blood will be collected

before the procedure for a platelet function assay (PFA), so participants with prolonged bleed times will also not undergo colonoscopy.

More common risks of colonoscopy include abdominal discomfort, bloating, transient fever, diarrhea, and constipation. Preparation for colonoscopy may cause dehydration.

The procedure will be performed by an experienced physician gastroenterologist who specializes in GI diseases and is experienced with endoscopy. As a general practice, the risk of the procedure is minimized by monitoring pulse, blood pressure, and oxygen saturation throughout the procedure and by providing inpatient monitoring after the procedure. Any complication will be identified as soon as possible and treated appropriately.

Anesthesia: Participants will receive conscious sedation or general anesthesia for colonoscopy, depending on the preference of the endoscopist. Sedative drugs will be provided by the Critical Care Medicine Department and/or experienced anesthesiologists of the NIH CC.

Side effects from sedative medications may include cardiovascular and respiratory depression, bradycardia, hypotension, respiratory acidosis, apnea, and hypersensitivity reactions. Stinging or pain may occur at the injection site.

Side effects from conscious sedation include post-procedure drowsiness, cardiovascular and respiratory depression, hiccoughs, headache, and nausea.

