8.2 STUDY EVALUATIONS & PROCEDURES

Targeted physical exam: The components of the exam will be at the discretion of the investigator. Weight and vital signs will be measured.

Baseline questionnaire: This will include questions regarding demographics, medical history, and medications. Participants may complete this questionnaire on paper or electronically via REDCap system.

Survey: A brief survey containing questions regarding diet and other factors that can affect the gut microbiome will be administered at each visit. Participants may complete this questionnaire on paper or electronically via REDCap.

Colonoscopy: Colonoscopy is an optional procedure for collection of intestinal biopsies and brushings. This procedure will be limited to those 30 years of age or younger. This is because the chance of incidental findings such as intestinal polyps are lower at this age.⁽³⁹⁾ If an incidental polyp was found, a polypectomy may need to be carried out at the discretion of the gastroenterologist performing the procedure, and this increases the risk of a colonoscopy.

Up to 20 research biopsies may be obtained from the colon and ileum. If a participant agrees to this procedure, then they will undergo it at baseline and the day 8 visit. Baseline has a window between weeks -18 and -1, so it will be scheduled relative to day 0 so there are at least 30 days between colonoscopy procedures. Colonoscopy preparation will be per standard process, and participants will be instructed accordingly. Before the first procedure to ensure participant safety,

participants will have a GI consultation, a pre-anesthesia consultation, clinical blood evaluations (section 8.2.1), and a pregnancy test (if of childbearing potential); an ECG and chest X-ray may be conducted if they are determined to be needed per the Department of Perioperative Medicine guidelines at the NIH CC. These procedures, except the pregnancy test, will only be repeated up to 8 days before the second procedure if there are more than 30 days between colonoscopies and if they are determined to be needed per the Department of Perioperative Medicine guidelines at the NIH CC. A pregnancy test will always be done before both colonoscopies for participants who can get pregnant. Biopsies and brushings will be collected for research purposes, as described in section 8.2.1.

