9.3.1 Evaluable for Toxicity

All participants will be evaluable for toxicity from the time of their first treatment with BSS.

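### Section 9.4.4 plans no safety analysis for a reason that covers only the drug, and the sole harm population starts at least 19 days after the baseline research colonoscopy

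*Combined protocol and SAP*

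**What the plan says.** Section 9.4.4 gives its position in one sentence: "As this study uses BSS, an already FDA-approved OTC medication, there are no safety endpoints that will be analyzed". It then refers to ongoing assessment under 8.3 and adds Table 2, which gives early-stop probabilities for the first 10 participants. Section 8.3 describes review during the study and return of results to participants, not a summary of events.

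One population is defined for harms, in 9.3.1: "All participants will be evaluable for toxicity from the time of their first treatment with BSS". In the Schedule of Activities (1.3) the AE-assessment row is marked at days 0, 2, 8, 14 and 28, and not at screening or baseline.

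The study also offers research colonoscopy. Section 8.2 says: "This procedure will be limited to those 30 years of age or younger"; "Up to 20 research biopsies may be obtained from the colon and ileum"; and "If a participant agrees to this procedure, then they will undergo it at baseline and the day 8 visit". Section 2.3.1 adds: "Participants will receive conscious sedation or general anesthesia for colonoscopy". It lists perforation, severe bleeding and serious infection as rare serious risks. On timing, 8.2 says of the baseline procedure "so it will be scheduled relative to day 0 so there are at least 30 days between colonoscopy procedures", and footnote a of 1.3 refers to "the required 30-day interval between the optional colonoscopies at baseline and day 8".

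**The concern.** Approved over-the-counter status is a reason for modest safety analysis of a 2-day labelled dose. It says nothing about colonoscopy, biopsy, bowel preparation or sedation, which carry the most serious risks that 2.3.1 describes for participants who choose them. Section 2.3.2 says participants will not benefit.

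Two things follow if the plan is carried out as written. First, no section commits the study to a named summary of AEs, serious AEs (SAEs) or AESIs in its results. Second, a harm table built on the 9.3.1 population would leave out events after the first colonoscopy, because that procedure comes before dosing. It would also leave out anyone who had that procedure and never received BSS. Section 7.2 shows how this can happen: a participant who becomes pregnant before day 0 is withdrawn. What is at stake is how completely harms are reported, not the microbiome result.

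**Working it through.** **Figures in 9.4.4.** The section's only numbers are in Table 2: the probability of at least one participant with an AE in the first 10, which is 1 - (1 - p)^10. For p = 0.01, 0.05, 0.10, 0.2, 0.3 and 0.4 this gives 0.096, 0.401, 0.651, 0.893, 0.972 and 0.994. The table prints 0.10, 0.40, 0.65, 0.80, 0.97 and 0.99. Five of the six cells reproduce; the cell at p = 0.2 should read 0.89. That slip is a separate matter. For this point, what counts is that Table 2 describes a stopping rule in advance and does not summarize observed events.

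**When the baseline colonoscopy can occur.** Inputs: the second colonoscopy is at day 8 (±3), so day 5 to 11 (1.1, 1.3); the procedures are at least 30 days apart (8.2; 1.3 footnote a); the baseline window opens at week -18 (1.3); first dose is on day 0.

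Latest baseline day = day of second colonoscopy - 30.

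- Second on day 11: 11 - 30 = day -19
- Second on day 8: 8 - 30 = day -22
- Second on day 5: 5 - 30 = day -25

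Earliest baseline day: -18 × 7 = day -126.

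The 9.3.1 population and the 1.3 AE row therefore begin 19 to 126 days after the baseline colonoscopy. A participant who has both procedures has 1 of 2 before either begins.

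**Whether another section supplies the summary.**

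| Section | What it provides | Names an AE summary? |
|---|---|---|
| 7.2 | Keeps replaced participants' data for a safety assessment whose output is not defined | No |
| 8.3 | Ongoing review | No |
| 8.4.3, 8.4.8, 10.5.1, 10.5.2 | AESI definition, reporting to the Clinical Safety Office (CSO), periodic surveillance, medical monitor | No; this is oversight during the study |
| 8.4.5 | AE elicitation at each contact; all events in source documents, reportable ones in CRIMSON | No; this is collection |
| 9.4.1 | Means or proportions with 95% intervals, in general terms | No |
| 9.4.6 | Individual data listed by measure and time point | No |

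Sections 9.4.1 and 9.4.6 could be read to include AEs, but 9.4.4 deals with safety specifically and declines analysis. A listing also fixes no denominator.

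**Consistency of 1.3 with 8.4.5.** Section 8.4.5 asks about AEs at each contact, and the baseline visit is a contact. The AE row in 1.3 leaves that column empty. The two sections disagree on the visit that holds the first colonoscopy.

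**The case against.** Section 3 lists no safety objective or endpoint, so the sentence in 9.4.4 describes the design accurately. In a single-arm exploratory study of 20 people taking a labelled dose for two days, an unnamed AE table may seem a small omission. Sections 9.4.1 and 9.4.6 do not exclude AEs, and at this sample size counts can be read from a listing. Colonoscopy harms have a track of their own that does not depend on dosing: the AESI definition, CSO reporting and surveillance, the medical monitor, and pausing and halting rules that cover study procedures. Section 9.3.1 does not restrict collection, and day 0 is itself an AE assessment after the baseline procedure.

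Most of this stands, and it rules out two stronger readings. A reader might infer that harms from the baseline colonoscopy go uncollected or unwatched. The documents do not support that: 8.4.5 and the AESI rules cover them. A reader might also infer that the study will produce no account of harms at all. That goes too far, because the generic listing and summary provisions, together with the safety assessment in 7.2, could yield a partial one.

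What the objection does not answer is that the stated reason omits the procedures, that no section names a summary, and that the one stated harm population excludes the first procedure and the never-dosed. The safety review and communications plan is not among the documents, so what it tabulates is unknown. Section 10.5.1 describes it as an internal document, not as part of the planned results.

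**Conclusion.** The point holds as a minor gap in planned reporting. Section 9.4.4 declines safety analysis for a reason that does not reach the research colonoscopies. The only harm population starts 19 to 126 days after the first of them.

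The size is limited. It concerns only participants who choose colonoscopy, who must be 30 or younger, and uptake is not stated, so the number affected is unknown. The 1-in-2 figure is scheduling arithmetic for a participant who has both procedures; it should not be read as half of procedure harms being lost. The primary conclusion is unaffected. The result rests on the 30-day minimum and the day 8 (±3) window being followed, and on reading the specific statement in 9.4.4 as governing the general ones in 9.4.1 and 9.4.6.

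**What to change.** Replace the quoted sentence in 9.4.4 with wording such as:

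> No safety endpoint is tested. AEs, SAEs and AESIs will be summarized descriptively as number and percentage of participants, by highest grade and relatedness, with exact 95% confidence intervals.

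Keep the sentence on ongoing assessment that follows it. Then define two denominators:

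- **BSS events:** from first dose, in the 9.3.1 population.
- **Colonoscopy-related events** (procedure, biopsy, sedation, bowel preparation): from the first study procedure, including bowel preparation, among all participants who began it, dosed or not.

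In 1.3, mark AE assessment at baseline for colonoscopy participants, so that it agrees with 8.4.5.

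The cost is low, but it is more than a wording change. There will be one or two extra tables. Only reportable AEs are entered in CRIMSON (8.4.5), so other events must be abstracted from source documents. Section 8.4.4.2 defines relatedness to the study intervention, so relatedness to study procedures must be recorded as well; 7.1.1 and 8.4.3 already require that judgment for some events. No visit or participant is added.

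Intervals will be wide. With no events, the exact two-sided upper limit is 1 - 0.025^(1/n): 16.8% for n = 20, and 30.9% if 10 people have a colonoscopy (an assumed number, for illustration).

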7 STUDY INTERVENTION DISCONTINUATION AND PARTICIPANT DISCONTINUATION/WITHDRAWAL

7.1 DISCONTINUATION OF STUDY INTERVENTION

Study intervention may be discontinued for an individual participant (ie, pausing), or it may be discontinued for all participants and enrollment suspended (ie, halting). Pausing and halting rules and procedures are described below.

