7.1.1 Pausing Rules for an Individual Participant

Pausing is the suspension of administration of study agent to a single participant until a decision is made whether to resume administration of the study agent.

The pausing criteria for a single participant in this study include any of the following:

- A participant experiences a grade 3 or higher AE that is unexpected and is possibly, probably, or definitely related to the study agent or study procedures.
- A participant experiences an SAE that is unexpected and is possibly, probably, or definitely related to the study agent or study procedures.
- Any safety issue that the investigator determines should pause administration of the study agent to a single participant.

The principal investigator will determine if study agent administration should be paused.

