7.1.2 Halting Rules for the Protocol

Halting the study requires immediate discontinuation of study agent administered for all participants and suspension of enrollment until a decision is made whether to continue enrollment and study agent administration.

The halting rules are:

- Two or more participants experience the same or similar grade 3 or higher AEs that are unexpected and possibly, probably, or definitely related to the study agent or study procedures.
- Two or more participants experience the same or similar SAEs that are unexpected and possibly, probably, or definitely related to the study agent or study procedures.
- Any safety issue the investigators determine should halt the study.

The principal investigator will determine if the study should be halted. The IRB may halt the study at any time.

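### Table 2 prints 0.80 where its own formula gives 0.89, and it labels the chance of at least one pausing event as an early stop for any adverse event

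*Combined protocol and SAP*

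**What the plan says.** Section 9.4.4 (Safety Analyses) refers to the AEs covered by the pausing rules of section 7.1.1 and then states: "Table 2 below lists the early stop probabilities for the first 10 participants". The table is titled "Probability of Early Stop for Possible True Probabilities of Any Adverse Event in the First 10 Participants", and its result row is "Prob. of ≥ 1 with any AE in the first 10 participants". The columns are true probabilities of 0.01, 0.05, 0.10, 0.2, 0.3 and 0.4. The printed results are 0.10, 0.40, 0.65, 0.80, 0.97 and 0.99.

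Section 7.1 separates two actions. Pausing applies to one person: "Pausing is the suspension of administration of study agent to a single participant until a decision is made" (section 7.1.1). Its first criterion is "A participant experiences a grade 3 or higher AE that is unexpected and is possibly, probably, or definitely related" to the agent or procedures. The others are an unexpected, related SAE and any safety issue for which the investigator judges a pause is needed. Halting is the study-level action, under which the intervention is stopped more widely: "it may be discontinued for all participants and enrollment suspended (ie, halting"). Its first count-based trigger in section 7.1.2 is "Two or more participants experience the same or similar grade 3 or higher AEs that are unexpected" and related; the second is the same rule for SAEs. There is also a discretionary trigger: "Any safety issue the investigators determine should halt the study".

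**The concern.** There are two separate problems in one small table.

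First, the 0.2 column breaks the pattern of the row. Going from 0.65 at p = 0.10 to 0.80 at p = 0.2 and then 0.97 at p = 0.3 is not what a single binomial formula with 10 participants produces.

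Second, the title and row labels describe something other than what is calculated. One event among 10 participants triggers a pause in that participant, not a stop of the study. And the events that count are the restricted set in section 7.1.1, not every adverse event. Section 8.4.1 defines an AE with no severity or relatedness threshold. Temporary stool darkening, which section 2.3.1 lists as a known reaction, could therefore be counted under the table's wording although, being expected, it meets neither the AE nor the SAE pausing criterion.

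An IRB or safety reader could take away a wrong number at p = 0.2, or read the row as the chance that the study stops.

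**Working it through.** **Inputs.** From section 9.4.4: n = 10 participants, a threshold of at least one participant with an event, and the six true probabilities. Assumption: participants are independent and share the same event probability p.

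**Step 1: reproduce the printed row.** P(at least 1 of 10) = 1 − (1 − p)^10.

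| p | Computed | Printed | Agrees |
|---|---|---|---|
| 0.01 | 0.0956 | 0.10 | yes |
| 0.05 | 0.4013 | 0.40 | yes |
| 0.10 | 0.6513 | 0.65 | yes |
| 0.2 | 0.8926 | 0.80 | no |
| 0.3 | 0.9718 | 0.97 | yes |
| 0.4 | 0.9940 | 0.99 | yes |

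Five cells agree to two decimals, which confirms both the formula and n = 10. At p = 0.2, 0.8^10 = 0.107 and 1 − 0.107 = 0.893. The printed value is low by 0.893 − 0.80 = 0.093, too much for rounding.

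**Step 2: look for another reading that gives 0.80.**

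- A different n at p = 0.2: n = 7 gives 0.790 and n = 8 gives 0.832. No integer n gives 0.80, and n = 7 or 8 would also spoil the other columns (n = 8 gives 0.57 at p = 0.10, for example).
- A threshold of two events in 10 at p = 0.2 gives 0.624.
- A different p with n = 10: solving 1 − (1 − p)^10 = 0.80 gives p = 1 − 0.2^(1/10) = 0.149. At p = 0.15 the formula gives 1 − 0.85^10 = 0.803.

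So either the entry is wrong, or the column was meant to be 0.15.

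**Step 3: compare the label with the rules.** The formula is the right one for the event that at least one participant meets a pausing criterion, provided p is the probability of such an event. It is not the probability of a study-level stop under the count-based triggers, which need two or more participants. For those, P(at least 2 of 10) = 1 − (1 − p)^10 − 10p(1 − p)^9:

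| p | At least 1 (pausing) | At least 2 (ceiling for the count-based halting triggers) |
|---|---|---|
| 0.01 | 0.096 | 0.004 |
| 0.05 | 0.401 | 0.086 |
| 0.10 | 0.651 | 0.264 |
| 0.2 | 0.893 | 0.624 |
| 0.3 | 0.972 | 0.851 |
| 0.4 | 0.994 | 0.954 |

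The last column is an upper bound, because the two events must also be the same or similar. It does not bound halting overall, since section 7.1.2 also allows a discretionary halt with no minimum count.

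**The case against.** The cell error has no good defence: nothing elsewhere in the document corrects it. A digit misread when the PDF was converted cannot be fully excluded, but the table came through with six headers and six values in order.

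The labels can be defended in part. The lead-in sentence cites section 7.1.1, so any AE can be read as shorthand for any of those AEs. Section 7.1 itself describes a pause as discontinuing the intervention for one participant, so an early stop could mean stopping the agent in that person. Section 9.4.4 does not mention halting, and the row label says plainly that it counts at least one event in 10. A careful reader can therefore recover the intended meaning. That softens the point but does not remove it: the title read alone says something else, and the protocol does not define early stopping.

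The 0.15 column is also only a possibility. The printed header fits the run 0.2, 0.3, 0.4, and a simple slip for 0.89 explains the cell equally well.

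Finally, the error runs toward understating how often an event would be seen, so it does not flatter the rule. The table drives no decision; pausing and halting are for the principal investigator to determine, and the IRB may also halt the study.

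**Conclusion.** Both parts hold, and the point is minor. The 0.2 cell should read 0.89. The printed 0.80 is 0.093 too low, about 10% of the correct value (0.093 / 0.893). Put the other way, the implied chance of seeing no pausing event in 10 participants is 0.20 as printed against 0.107, a ratio of 1.9. This rests only on independent participants with a common event probability, which the other five cells show the plan also used.

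The title and row labels misdescribe the quantity. A reader who takes the row as the chance of a study stop would overstate the count-based halting triggers considerably at low event rates: 0.40 against at most 0.09 at p = 0.05, and 0.65 against at most 0.26 at p = 0.10.

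No endpoint, sample size or study procedure depends on the table, and the pausing and halting rules are clear as written.

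**What to change.** Edit section 9.4.4 only.

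1. Change 0.80 to 0.89 in the 0.2 column. If the authors' own working shows that 0.15 was the intended column, change the header to 0.15 and keep 0.80.
2. Retitle the table and its result row along these lines: *Probability that at least one of the first 10 participants has an event meeting a pausing criterion (section 7.1.1)*. Relabel the header row as the true probability of such an event, and replace the early-stop wording in the lead-in sentence to match.
3. Optional, if study-level stopping is to be described: add a row for P(at least 2 of 10), stated as an upper bound for the count-based triggers of section 7.1.2 only.

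The cost is one cell (or one column header) and a few words of labelling. No rule, sample size or procedure changes.
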